[name], Ph.D, obtained his doctorate under [name], and has extensive experience and background in clinical TMS and taVNS, especially in the development of novel protocols for neurological disorders. His thesis work involves systematic elucidation of the dose response of taVNS on heart rate, use of heart rate as a biomarker of taVNS effect, and the use of taVNS with fMRI in determining pathways and regions affected by taVNS in adults. He determined that the 'on' pulse heart rate change was a mean of -3 beats per minute (bpm) while the 'off' pulse heart rate change was +6 bpm. Although these are statistically significant and measurable changes, they are physiologically insignificant. Nevertheless, this will be an important biomarker for infants, but is not expected to result in safety concerns. [name] careful and thorough studies lay the safety and efficacy groundwork for the current proposal.

D. RESEARCH DESIGN AND METHODS (including data analysis)

Due to the novelty of these studies, [name] will be present for each taVNS-paired feeding session conducted in the first participants, and as needed thereafter. [name] and or [name] will monitor taVNS effects. If any adverse events are noticed which are not described in the consent or are serious, we will inform the IRB before continuing with the next enrolled subject. Importantly, all of these methods have been done before, and published by our and other groups in adults, and we believe these extra precautions will assure the safety and well-being of any participants enrolled.

taVNS-paired feeding to enhance feeding behavior in neonates

Screening

Prospective participants will be identified by the PI ([name]) at the MUSC neonatal intensive care units (Level II and III), and checked for potential inclusion (please see the uploaded taVNS screening form). [name], and other clinical OTs based in the nursery may also mention the study to parents and refer them to [name] if they are interested in participating.

Participants

Inclusion criteria:

Infants must be clinically stable, on minimal respiratory support (nasal cannula, or room air), in discussions about Gtube placement for poor po feeding and are currently greater than or equal to 39 weeks post-menstrual age and

- 1) If born premature have been working on oral feeding for 30days;
or

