- 2) If term Infant with significant medical issues that have precluded oral feeding, such as hypoxic ischemic encephalopathy (HIE), have been working on oral feeding for 14days.

Exclusion criteria:

- 1) Unstable infants or those requiring respiratory support involving positive pressure.
- 2) Major unrepaired congenital anomalies
- 3) Anomalies/conditions that limit feeding volumes
- 4) Cardiomyopathy
- 5) Repeated episodes of autonomic instability (apnea or bradycardia) which are not self-resolving *

*Preterm infants commonly have short periods of shallow or absent breathing or lower heart rate termed apnea and bradycardia, respectively, and most are being treated for these physiologic manifestations of prematurity with caffeine, an effective central stimulant. Infants are on cardiorespiratory monitors through the nursery stay to capture events, many of which are self-resolving. Infants who require repeated episodes of tactile stimulation to come out of these events are defined as *unstable*.

Neonates who are beginning oral feeds after medical treatment for critical illnesses, such as HIE brain injury, will be included as these neonates represent a population in which taVNS-paired feeding could present the largest success in overcoming impaired brain development. Congenital syndromes may be included if the infants do not have major, unrepaired anomalies or anomalies that limit feeding volumes.

Written informed consent will be obtained from the mother if available and if she has custody or decision making authority for the participant, otherwise a parent or legal guardian, prior to participation in the experimental paradigm. Department of Social services may have custody of infant but require the parent or foster parent to consent for all medical procedures.

Electronic Consent will be used for situations when the parent (or Legally Authorized Representative) is at another hospital and cannot travel to MUSC to provide consent in person. We will use the approved REDcap system to obtain consent. [name] or other approved study personnel will go over the entire consent document on the phone with the parent to ensure comprehension and to confirm identity. Parent will be given a copy of the completed, signed consent form in person or by email or fax.

Study Design

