Up to 40 preterm/HIE neonates will be enrolled in this prospective, open-label safety and feasibility trial, with a dose response. The experimental paradigm consists of 2 to 3 weeks of once or twice daily taVNS-paired feeding.

Our control group was investigated by Drs. [name] and [name] at MUSC, who have researched all infants failing feeding and getting Gastrostomy tubes in our nurseries over the past 5 years. We can compare our data to this historical group at our own institution.

All consented participants will receive the active stimulation condition.

taVNS Stimulation (in Detail)

After obtaining consent and describing this procedure to the parents and all members of the baby's care team, we will first, with a 500 μ s, 25Hz pulse, gradually increase the intensity of the TENS unit until the baby can first feel something in their ear. We will use the facial expression change and fidgety movements to determine when the infants feel the stimulation. This intensity will be recorded as the perceptual sensory threshold. The stimulation intensity we will use for this study on taVNS-paired feeding is a small decrement from the perceptual sensory threshold for each infant (-0.1mA), a point at which they should not react to the stimulation. We will retest the sensory threshold before every session.

Determination of Perceptual Threshold

1. Electrode clip will be placed on the left tragus in an enrolled infant at rest. Starting at 0.2mA at 25Hz, we will deliver 5 seconds of pulses, and increase by 0.1mA until the perceptual threshold is achieved by observation of the infant's facial expression, fidgety movements, or NIPPS score. This will be termed the perceptual threshold.
2. We will then deliver this level of microcurrent while the infant is feeding on the first day to determine if the perceptual threshold changes with feeding. Current will then be held constant while pulse width and frequency will be set at 500us and 25Hz, respectively.

3. Finally, we will decrease the microcurrent by 0.1mA *below the perceptual threshold* and administer this taVNS treatment during the feeding and deliver this only while the infant is actively sucking from the bottle.
4. The total duration of this 'on-and-off' taVNS stimulation treatment will continue for 30 minutes or the duration of the feed.
5. We may manually trigger the taVNS stimulation or place a gel EMG electrode over the temporomandibular joint area to trigger the taVNS impulse.

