For safety we will compare HR changes from baseline to during taVNS within subjects. We will compare treatment before and after the taVNS-paired feeding treatment for the rate of feeding volume increase, and days to full po feeds. We will use repeated measures ANOVA to analyze repeated measures such as HR over 5 minutes and mean daily feeding volumes in 7-10 day epochs. We will analyze the number of infants who reach full feeds vs requiring G-tube during taVNS-paired feeding, between once and twice daily stimulation by Chi-squared. We will assess differences in kurtosis parameters from pre-to post taVNS scans by paired t-test, and between those that reach full oral feeds vs those that require a Gtube by unpaired t-test.

Estimated Difficulties, Limitations and Time Frames

Estimated Difficulties. Many of the initial parameters for taVNS in humans, such as frequency and pulse width, were accomplished in trials at MUSC by [name] et al. that were approved by the IRB. In one sense, we will be shrinking many of the components into miniature form to deliver stimulation to neonates and infants. In spite of the clear differences in size and skin between the neonatal and adult ear, the custom electrodes have been fitted to several different weights of infants (2.5-4.0 kg).

Limitations. We will not be delivering a SHAM stimulation paradigm (electrodes and Digitizer with appearance of taVNs treatment without actual current). Our goal is to determine safety and feasibility of active treatment with a dose response in order to investigate whether this should be administered in a larger randomized control trial. In this respect, the comparison we lose in not having a SHAM stimulation is offset by the validation we will receive in the safety and feasibility of active treatment. We will compare our overall results with characteristics of infants who required a Gtube from [name] and [name]'s publications.

Estimated Time Frames. The duration of the study will likely be ~4 years, with 2 years of active enrollment and 18 months of follow-up.

E. PROTECTION OF HUMAN SUBJECTS

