1. RISKS TO THE SUBJECTS

The human subjects involved in this research will be preterm neonates or infants with critical illnesses that preclude oral feeding, such as HIE. Inclusion criteria involves 2 main groups. The first is comprised of typical pre-term, high risk neonates who are in the convalescent near and post-term period and learning to po feed. The second is comprised of neonates that present after severe medical illnesses or brain injury. In both cases, the infants can only be enrolled if they are stable, not making progress with OT training, and are in discussion for Gtube placement. Participants will be excluded if they have major unrepairs congenital abnormalities that limit volume of feeds, cardiomyopathy, significant autonomic instability, such as repetitive, unresolved bradycardia or apnea, or use a continuous positive airway pressure (CPAP) device or other form of high respiratory support preventing them from breathing without assistance.

Targeted/Planned Enrollment Table

Total Planned Enrollment: 40 babies (active)

TARGETED/PLANNED ENROLLMENT: Number of Subjects receiving active taVNS			
Ethnic Category	Sex/Gender		
	Females	Males	Total
Hispanic or Latino	4	5	9
Not Hispanic or Latino	15	16	31
Ethnic Category: Total of All Subjects*			

Racial Categories			
American Indian/Alaska Native			
Asian			
Native Hawaiian or Other Pacific Islander			
Black or African American	8	7	15
White	12	13	25
Racial Categories: Total of All Subjects*	20	20	40

*The “Ethnic Category: Total of All Subjects” must be equal to the “Racial Categories: Total of All Subjects”.

Volunteers of all ethnicities and racial categories will be accepted into this study protocol. No preference will be given based on race, gender or ethnicity. No vulnerable populations or special classes of subjects will be considered for participation.

b. Sources of Materials

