2. ADEQUACY OF PROTECTION AGAINST RISKS

a. Recruitment and Informed Consent

This information is listed on the eIRB website.

b. Protection against Risk

The following risks are present with this study: Risk of skin irritation, risk of discomfort, risk of slightly decreased heart rate, and risk of loss of confidentiality.

Risk of skin irritation: we will monitor the skin on the inner aspect of the left ear before and after each session, and will switch to the right ear if redness is present, and decrease the stimulation if redness persists.

Risk of discomfort: We expect to be able to use the pain ratings scales to identify the perception of tingling versus pain with taVNS in these infants. We will use facial expression change, fidgety movements and infant behavioral discomfort using our standard neonatal pain scale (NIPS) with the bedside nurse at the start and after 5 minutes of taVNS, at 10 minutes and at the end of treatment. We will protect against the risk of discomfort by close monitoring and by the determination of perceptual threshold using the protocol outlined above.

We will hold the treatment for a NIPS score of >3 , until discomfort subsides, and resume at a lower stimulus level if this level of discomfort recurs. We do not expect the infant to cry at this level, but show discomfort in brow furrowing, grimace, etc. Feeding is generally comforting for infants, and we expect to see minimal pain response to treatment. Infants are fed sidelying in the nursery. We will position the baby so that the left ear is facing up, and we can monitor the site and pain without disturbing the feeding process unduly.

Risk of slightly decreased heart rate: we will monitor HR, respiratory rate and oxygen saturation continually during the feeding to monitor these physiologic responses to taVNS-paired feeding. The infants' vital signs are constantly monitored as standard of care while in the nursery. We will print out values at baseline, and changes with feeding and taVNS-paired feeding. Normal heart rate is 120-170 beats per minute in preterm infants feeding, and 110-140 bpm in term HIE infants. As HR usually accelerates with motor activity of feeding, we do not expect significant bradycardic HR changes during the 'on' pulse. However, if the HR decreases to <100 bpm during 'on' pulse, or if HR rebound is >190 bpm during 'off' pulse, we will hold treatment and start again at a lower stimulation level.

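### The two between-infant tests (full feeds by once vs twice daily, and kurtosis by feeding outcome) have no birth-group term, so preterm vs term/HIE case mix can confound both

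*Combined protocol and SAP*

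**What the plan says.** Study Design (section D) says: "Up to 40 preterm/HIE neonates will be enrolled", in an open-label study of safety and feasibility that also looks for a dose response. It adds: "The experimental paradigm consists of 2 to 3 weeks of once or twice daily taVNS-paired feeding". It does not say how an infant comes to be treated once or twice daily.

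Section E.1 acknowledges two populations: "Inclusion criteria involves 2 main groups". The inclusion criteria set different thresholds. For preterm infants: "If born premature have been working on oral feeding for 30days". For term infants with major medical problems such as HIE: "have been working on oral feeding for 14days". Both must be at least 39 weeks post-menstrual age. Section E.2b also gives them different reference ranges: "Normal heart rate is 120-170 beats per minute in preterm infants feeding, and 110-140 bpm in term HIE infants". The enrolment table splits the 40 infants by sex, ethnicity and race, but not by birth group.

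Data Analysis (section D) plans:
- heart-rate change within infants, feeding before and after treatment, and repeated measures ANOVA for heart rate and daily volumes;
- a chi-squared test of full feeding or G-tube by once or twice daily treatment, an outcome that Specific Aim 1 lists as primary;
- a paired t-test of kurtosis before and after treatment, and a comparison "between those that reach full oral feeds vs those that require a Gtube by unpaired t-test".

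No test names birth group as a factor, stratum, covariate or subgroup.

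**The concern.** Two of these tests compare different infants, so a characteristic that differs between the compared sets can produce a difference by itself. Birth group is an obvious candidate. The protocol defines the groups separately, admits them after different periods of failed oral feeding, and in section A explains their feeding difficulty differently: underdeveloped muscles in preterm infants, interrupted development of cortex and basal ganglia in HIE.

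Feeding outcome is observed, not assigned. If preterm and term/HIE infants differ both in reaching full feeds and in kurtosis, the unpaired t-test partly compares birth groups. Even random dose allocation would not protect it. The dose test is exposed because no allocation rule keeps the birth-group mix similar at the two doses.

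The protocol says that results on safety, feasibility and dose response will inform whether to run a larger randomised trial. A case-mix difference read as a dose effect or as a brain correlate of feeding success would misdirect that decision.

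**Working it through.** The plan gives no alpha, power, event rate, SD or sample-size derivation, so there is no figure of its own to reproduce. Its only numerical input is the cap of 40 infants. All rates, mixes and gaps below are assumptions, and the nominal level is taken as 5%.

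**Dose test (chi-squared, 20 vs 20, no true dose effect).** Let m1 and m2 be the preterm shares at the two doses, and pP and pH the full-feed rates in preterm and HIE infants. The spurious difference is (m1 − m2) × (pP − pH). With shares of 70% and 30% and rates of 65% and 35%:
- one dose: 0.70 × 0.65 + 0.30 × 0.35 = 0.56;
- other dose: 0.30 × 0.65 + 0.70 × 0.35 = 0.44;
- difference: 0.40 × 0.30 = 0.12.

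Exact type I error of the unstratified test:

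| Full feeds, preterm vs HIE | Preterm share 50/50 | 60/40 | 70/30 | 80/20 |
|---|---|---|---|---|
| 60% vs 40% | 0.038 | 0.045 | 0.065 | 0.100 |
| 65% vs 35% | 0.033 | 0.047 | 0.093 | 0.177 |
| 70% vs 30% | 0.026 | 0.050 | 0.133 | 0.291 |

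A Mantel-Haenszel test stratified by birth group gives 0.043-0.052 in all these settings (100,000 simulations each). For scale, if 20 preterm and 20 HIE infants were randomised 20 to each dose, a split at least as uneven as 60/40 would occur with probability 0.34, and one at least as uneven as 70/30 with probability 0.026. Clear inflation therefore needs non-random allocation or an unlucky draw.

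**Imaging test (unpaired t-test on kurtosis levels, no link with feeding within birth group).** Take 20 preterm and 20 HIE infants, full feeds in 70% and 40%, and a 1 SD kurtosis gap:
- preterm share among full feeders: 0.70 / (0.70 + 0.40) = 0.636;
- preterm share among G-tube infants: 0.30 / (0.30 + 0.60) = 0.333;
- spurious difference: (0.636 − 0.333) × 1 SD = 0.30 SD;
- expected group sizes: 22 and 18;
- variance within outcome groups: 1 + (22 × 0.636 × 0.364 + 18 × 0.333 × 0.667) / 40 = 1.227, so SD 1.108;
- standard error: 1.108 × √(1/22 + 1/18) = 0.352;
- ratio: 0.303 / 0.352 = 0.86. A noncentral t with 38 degrees of freedom then rejects in about 13% of trials.

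Simulations agree with this approximation:

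| Infants | HIE share | Full feeds, preterm vs HIE | Gap (SD) | Unadjusted false-positive rate |
|---|---|---|---|---|
| 40 | 50% | 70% vs 40% | 1.0 | 0.13-0.14 |
| 40 | 50% | 70% vs 30% | 1.0 | 0.20-0.21 |
| 40 | 50% | 60% vs 40% | 1.0 | 0.08-0.09 |
| 40 | 50% | 60% vs 40% to 70% vs 30% | 0.5 | 0.06-0.09 |
| 40 | 25% | 70% vs 40% | 1.0 | 0.10-0.11 |
| 20 | 50% | 70% vs 40% | 1.0 | 0.09 |
| 20 | 50% | 70% vs 40% | 0.5 | 0.06 |

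With birth group in the model the rate is about 0.05 throughout. With no kurtosis gap, the unadjusted test is also at about 0.05.

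**Within-infant tests.** A constant birth-group offset subtracts out of each infant's own difference. With offsets of 0, 1 and 2 SD, the paired t-test rejects in 0.047-0.051 of trials.

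**The case against.** The strongest reply is that most of the planned analyses are within infant. A reader might infer from the missing term that every analysis is biased, or that the different heart-rate ranges invalidate the heart-rate comparison. The documents do not support either inference. Heart-rate change, feeding before and after treatment, and the paired kurtosis test use each infant as its own control. There, pooling can hide different responses but does not create a false change from a fixed difference. The heart-rate ranges show that the populations differ; they do not enter the dose or imaging test.

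Second, the kurtosis sentence can be read as comparing pre-to-post change by feeding outcome. On that reading a fixed gap cancels (0.046-0.052 in simulation), and confounding needs birth groups that change at different rates. This stands, and the plan should say which quantity is compared.

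Third, no input comes from the documents, and smaller gaps or samples give slight inflation: at 70% vs 40% full feeds in 40 infants, half HIE, a 0.3 SD gap gives 0.060. All infants are at least 39 weeks, stable and being considered for a G-tube, which narrows the contrast. This limits the size of the problem but does not remove the mechanism.

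Fourth, this is a safety and feasibility pilot that ranks efficacy second and says it cannot determine G-tube avoidance. That lowers the stakes. But dose response is a stated aim, and an adjusted test is no harder to run.

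Finally, unspecified dose allocation is the deeper defect behind the dose comparison. Stratifying on birth group leaves other selection untouched. That is correct.

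**Conclusion.** The point holds for two tests: the once vs twice daily chi-squared test and the full-feeds vs G-tube comparison of kurtosis. Neither accounts for birth group, although the protocol itself defines two populations.

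The dose test is distorted only if birth group is both unbalanced across doses and related to full feeding. With balance it gives no false signal (0.026-0.038); in the settings examined, inflation becomes clear from about a 70/30 split. The imaging test is distorted only if birth group is related to both feeding success and kurtosis, or to kurtosis change if change is analysed.

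Across the tabulated assumptions, the unpaired t-test on levels has a false-positive rate of about 6-21%, against 5% with adjustment. The upper part of that range needs a 1 SD gap, and the documents neither confirm nor exclude one. The change is worth making because it is nearly free, not because a false finding has been shown to be likely.

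**What to change.** 1. Compare once and twice daily by a Mantel-Haenszel test stratified by birth group (preterm vs term/HIE), defined by the entry criterion each infant met. State how dose is assigned, since stratification does not correct other selection.
2. Replace the unpaired t-test with a linear model of kurtosis on feeding outcome plus birth group and, if wanted, post-menstrual age at scan. State whether the response is the level or the pre-to-post change.
3. In the repeated measures ANOVA, add a birth-group-by-time interaction if differences in response are of interest. A birth-group main effect alone leaves the within-infant time test essentially unchanged.

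The imaging model costs one degree of freedom for birth group, or two with post-menstrual age. Estimates become slightly less precise. Birth group is known at enrolment, so no new data, visits or infants are needed. The term stratum remains mixed, because the criteria also admit term infants with other serious conditions, so some confounding may remain.

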Feeding in neonates involves a sequence of sucking, swallowing, and breathing that requires coordination of the face, head, and neck muscles with the myelinated vagal regulation of the bronchi and the heart (11). In preterm neonates, the muscles needed to feed are underdeveloped, resulting in the need for OT rehabilitation to 'learn' feeding patterns. Preterm neonates' inability to feed effectively is the primary reason for prolonged hospital stays (12). In neonates with HIE, development of cortex and basal ganglia is interrupted, and depending on the severity, normal developmental plasticity is hindered, further contributing to their inability to feed (13). Both types of feeding difficulties involve complex motor learning, which requires integration of sensory and motor pathways. Treating oromotor difficulties during the learned task of feeding with noninvasive brain stimulation that promotes plasticity, poses a highly novel application of taVNS. Our major premise is that in babies at high risk for motor problems, simultaneously delivered brain stimulation via taVNS will boost motor cortical plasticity involved in a learned feeding task, leading to better feeding.

This protocol has 2 specific aims that will be investigated:

Specific Aim 1: Improved Motor Learning - We aim to investigate whether pairing taVNS with rehabilitation training of feeding behavior in preterm and HIE neonates will enhance and accelerate the learning of effective feeding behavior in a dose responsive manner. We call this treatment "taVNS-paired feeding." The primary outcome measures of taVNS-paired feeding will be daily oral milk feeding volume changes from before to during treatment, and number of infants reaching full oral feeds

between once and twice daily taVNS-paired feeding, duration to full feeds, as well as general motor functional impairment as measured by [name] Test of Early infant motor Performance (STEP). Our hypothesis is that taVNS-paired feeding for preterm neonates is feasible, safe and effective at reducing length of stay solely for feeding reasons, compared to historical controls. As part of our safety investigations with separate funding, we may perform taVNS during a clinical modified barium swallow study with pediatric speech language pathologists performing the study and compare 10 swallows with stimulation on and off to determine if taVNS affects swallowing parameters.

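### The historical controls are described as infants who got a G-tube, so they cannot support the Aim 1 length-of-stay hypothesis

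*Combined protocol and SAP*

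**What the plan says.** **The control group.** Section D, Study Design, attributes the control group to investigators "who have researched all infants failing feeding and getting Gastrostomy tubes in our nurseries over the past 5 years" and adds: "We can compare our data to this historical group at our own institution". The Limitations paragraph describes the comparator in the same way: "We will compare our overall results with characteristics of infants who required a Gtube". No other historical group is described for feeding or length of stay.

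**What it is used for.** The Aim 1 hypothesis includes the statement that the treatment is "effective at reducing length of stay solely for feeding reasons, compared to historical controls". The primary outcomes in Aim 1 are "daily oral milk feeding volume changes from before to during treatment, and number of infants reaching full oral feeds".

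**Who enters the trial.** The inclusion criteria ask for infants "in discussions about Gtube placement for poor po feeding". Section E, Risks to the Subjects, adds that they must be failing to progress with occupational therapy. None of this requires that a G-tube be placed.

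**What is analysed.** Data Analysis plans within-infant comparisons before and after treatment, and a comparison of "the number of infants who reach full feeds vs requiring G-tube during taVNS-paired feeding, between once and twice daily stimulation by Chi-squared". It names no endpoint, starting day, adjustment or method for the historical group.

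**How efficacy is ranked.** The Limitations say: "Our goal is to determine safety and feasibility of active treatment with a dose response". Section B calls feasibility the primary purpose and ranks the hypotheses on infant improvement behind safety and feasibility. The Potential Benefits section concedes that avoidance of a G-tube cannot be determined from this study.

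**The concern.** Data Analysis treats full oral feeding and G-tube as the two ends an infant can reach. The historical group contains only infants who reached the second. The treated group is a mixture: some infants will fail, and some might have fed fully without any stimulation. The two groups would then differ in mean stay even if the treatment did nothing, provided that full feeders and G-tube infants differ in length of stay.

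At stake is the one efficacy hypothesis that the protocol ties to historical controls. The trial is meant to inform whether a larger randomized trial should follow. A reader making that decision could take a length-of-stay difference against this group as evidence of effect, and the Limitations do not warn that the group was chosen by its outcome.

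**Working it through.** The plan gives no length of stay, full-feeding rate or effect size for the historical group, so there is no stated figure to reproduce. The working isolates what control selection does on its own.

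**Inputs**
- Treated infants: up to 40, all on active stimulation (Study Design).
- Controls: all with a G-tube, as described in Study Design and Limitations.
- q, the share of eligible infants who would reach full oral feeds without stimulation: not in the documents; assumed 5%, 10%, 20%.
- gap, mean stay of G-tube infants minus mean stay of full feeders: not in the documents; assumed 14, 28 and -14 days. The negative value is included because Section A says G-tubes are placed so that infants can go home, so these infants may not stay longer.

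**Length of stay with no treatment effect.** Let L_F and L_G be the mean stay of full feeders and of G-tube infants. Assume that each eligible infant ends as one or the other, and that eligible infants who fail stay as long on average as the historical G-tube infants.

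- Treated mean = q x L_F + (1 - q) x L_G
- Control mean = L_G
- Difference = q x (L_F - L_G) = -q x gap, where a negative value favours stimulation

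| q | gap = 14 days | gap = 28 days | gap = -14 days |
|---|---|---|---|
| 5% | -0.7 | -1.4 | +0.7 |
| 10% | -1.4 | -2.8 | +1.4 |
| 20% | -2.8 | -5.6 | +2.8 |

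For example, 0.20 x 28 = 5.6 days in favour of stimulation, and 0.20 x 14 = 2.8 days against it when the gap is negative. The sign follows the sign of gap, and the shift vanishes as q goes to zero.

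**What this leaves out.** A treated infant who fails may receive a G-tube later because of time spent in the trial. That delay would lengthen treated stay, but it is an effect of participation. It would remain with a well-chosen control group, so it is not counted here.

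**Full oral feeding, descriptive only.** As described, the control rate is 0% by construction. With no treatment effect, the expected number of treated infants reaching full feeds is 40 x q = 2, 4 and 8. The chance of at least one is 1 - (1 - q)^40, which is 87%, 98.5% and 99.99% for q of 5%, 10% and 20%. A side-by-side table would then show a treated rate above the control rate.

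**The case against.** The strongest reply is that this is an open-label safety and feasibility study which says so repeatedly. Efficacy is ranked second, G-tube avoidance is conceded to be beyond the study, and the Limitations admit the absence of a sham group and look to a later randomized trial. The wording about the historical group is also loose enough to be read as descriptive context. All of this stands and lowers the weight of the point. It does not remove it, because none of these statements withdraws the Aim 1 length-of-stay hypothesis, and the Limitations do not mention selection on the outcome.

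A second reply is that q may be close to zero. Entry requires at least 39 weeks post-menstrual age, 30 or 14 days of work on oral feeding, a G-tube discussion and lack of progress. The documents do not exclude a very small q, and the shift would then be very small. Nor do they show that q is small.

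Three stronger readings are tempting, and the documents do not support them:
- A reader might infer that the plan contains a biased significance test of full oral feeding. It does not. Its chi-squared test compares once with twice daily treatment, and control selection does not touch it or the before-versus-during analyses.
- A reader might infer that the length-of-stay comparison is tilted towards stimulation. The direction cannot be fixed, because the sign of gap is unknown.
- A reader might add delay in treated infants who fail to the bias from control selection. As shown in the working, that is a separate matter.

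**Conclusion.** The point holds for the length-of-stay hypothesis. The only historical feeding comparator is selected on the trial's failure outcome and cannot support a claim of shorter stay. On the stated assumptions, control selection alone moves the difference by between 5.6 days in favour of stimulation and 2.8 days against it. Both q and gap are assumed, so these figures illustrate scale and do not estimate the bias. For full oral feeding the point is narrower: no test is planned, but any descriptive comparison would be set against a rate of 0% that the group's definition guarantees.

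The safety and feasibility objectives and the planned within-trial analyses are unaffected. This should be fixed, but it is not a fundamental defect of the study. The conclusion rests on the protocol's own two descriptions of the group, which agree. The publications behind the series, and part of the text around Preliminary Studies, were not available and might describe it more fully.

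**What to change.** **Recommended.** Remove "effective at reducing length of stay solely for feeding reasons, compared to historical controls" from the Aim 1 hypothesis. Keep the G-tube series as description only. State in Limitations that the series was selected on the outcome, so that neither G-tube avoidance nor a length-of-stay effect can be inferred from it. This changes wording only. The cost is that the plan gives up a stated efficacy claim.

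**Optional alternative**, only if entry eligibility can be recovered from charts, which the documents do not show. Define the historical group as all infants in the same NICUs who met this trial's entry and exclusion criteria, whatever their later G-tube status. Start the clock at a comparable point in both groups, counting only historical infants who at that point were still in hospital with neither full feeds nor a G-tube. Name the comparison and its method in Data Analysis. The cost is a wider chart review, including a rule for identifying from the record when a G-tube was under discussion. The effect on the length-of-stay result could go either way, and any delay caused by taking part in the trial would remain.
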